3.1 Definition of Baseline

For the endpoints based on daily recordings in the eDiary, i.e. the migraine, headache, aura without headache and acute migraine medication endpoints, the baseline values will be based on the data recorded daily in the eDiary during the first 28 days following the screening visit.

For the actigraphy endpoints, the baseline values will be based on the data recorded daily by the wearable device during first 28 days following the screening visit.

For all other endpoints, baseline will be defined as the latest available valid measurement taken prior to the administration of IMP.

3.2 Definition of Trial Periods

Classification of concomitant medications and adverse events into trial periods is defined in Section 8, and Section 12.1, respectively. For other data, assessments from the Withdrawal visit and Unscheduled visits will be assigned to a nominal, i.e. scheduled visit (see Section 15.13).

The trial consists of the following periods:

- Screening Period (28-30 days): Starts at Visit 1 (End of Week -4) and continues until the beginning of Visit 2 prior to administration of the IMP (End of Week 0).
- Placebo-controlled Period (12 weeks): Starts at the beginning of Visit 2 IMP infusion (End of Week 0) and continues until the beginning of Visit 5 IMP infusion (End of Week 12), or, for the participants with no Visit 5 IMP infusion, until Week 12, or, for the participants withdrawn from the study prior to Week 12 visit, until Week 12 (84 ± 2 days after Visit 2 IMP infusion).
- Open-label Period (20 weeks): Starts at the beginning of Visit 5 IMP infusion (End of Week 12) and continues up to and including the Safety Follow-up visit (Week 32).

The definition of the Placebo-controlled Period implies that for participants in the all-participants-treated-follow-up set (APTS-FU), see Section 4 below for definition, adverse events and concomitant medications reported after withdrawal in the Placebo-controlled Period but before Week 12, will be allocated to the Placebo-controlled Period.

For the APTS-FU patients, the safety assessments, and concomitant medications data subsequently collected at the Safety Follow-up visit will be reported separately in data listings.

For patients who enter the Open-label Period, the safety assessments and concomitant medications data collected at the Safety Follow-up visit will be presented together with the safety assessments and concomitant medications data collected during the Open-label Period.

3.3 Definition of Withdrawal

Withdrawal from study

The group of participants who withdraws from the study in the Placebo-controlled Period prior to receiving the IMP in the Open-label Period will be described as withdrawals from the study during the Placebo-controlled Period. The complementary group will be described as having completed the Placebo-controlled Period.

Similarly, for the Open-label Period, the group of participants who withdraw from the study before EoT visit (end of Week 24) after receiving IMP in the Open-label Period will be described as withdrawals from the study during the Open-label Period and the complementary group will be described as having completed the Open-label Period.

Withdrawal from treatment

Withdrawal from the treatment in the Placebo-controlled Period or the Open-label Period is not possible because IMP is only administrated once at Baseline/Randomization visit or Visit 5. Note that the infusion interruptions or terminations before full dose is received are not related to withdrawal.

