5.4 Withdrawal Criteria from the Study and IMP

A patient must be withdrawn from the study if:

- the patient withdraws consent (defined as a patient who takes back consent); section 8.7 states how the patient's data will be handled
- the patient fails to comply with study procedures
- the patient is lost to follow-up (defined as a patient who fails to comply with scheduled study visits or contact, who has not actively withdrawn from the study, and for whom no alternative contact information is available [this implies that at least two documented attempts have been made to contact the patient])

A patient must be withdrawn from further treatment with IMP if:

- the patient has been randomized in error and has not received IMP
- any site personnel break the randomization code for that patient before the patient has entered in the open-label period
- the investigator considers it, for safety, lack of efficacy, and/or study compliance reasons, in the best interests of the patient that he or she be withdrawn from treatment
- the patient experiences an anaphylactic reaction or another serious and/or severe hypersensitivity reaction to the IMP infusion, as assessed by the investigator. If the event occurs during the infusion, the infusion must be discontinued immediately.

Patients who interrupt/terminate their IMP infusion are encouraged to complete the study to allow for application of treatment policy strategies (see section 4.5). Patients who withdraw from treatment with IMP will not be replaced.

6 Investigational Medicinal Product

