16.4 Patient Disposition

Patient disposition will be summarized by treatment group and include the number of patients in the APTS who completed or withdrew from the study for each period, as well as the number of patients in each analysis set. Note that withdrawal from treatment is not possible for the APTS patients, as they only receive the treatment on one occasion during the

placebo-controlled period. Withdrawal from study after IMP has been infused leads to missing data and the handling of these will be described in the SAP (see also section 16.8.1).

The number of patients who withdrew from the study will be summarized by treatment group and primary reason for withdrawal as well as by treatment group and all reasons for withdrawal.

The summary of patient disposition will be presented for each country and overall.

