Participants will attend on-site visits at Screening Visit, visits with IMP intravenous (IV) infusions (Baseline Visit and Week 12 Visit), and End-of-trial (EoT) visit at Week 24. All other visits will be conducted as telephone or telemedicine visits.

Participants will complete daily eDiary from Screening Visit until EoT/Withdrawal Visit.

Participants will receive BI and IMP (eptinezumab or placebo) at Baseline Visit during the Placebo-controlled Period and IMP (eptinezumab) at Week 12 Visit during the Open-label Period.

BI is a semi-structured educational conversation with the purpose on helping the participants to stop or reduce the medication overuse. The BI starts with five questions of the SDS:H (including an indication of the participant's willingness and confidence to change his/her medication overuse). Then participant is shown a short-structured scheme bases presentation either on a flip-over or slides with information about MOH and the association between medication overuse and chronic headache. The interview will end with an agreed plan on how to stop or reduce medication overuse (based on self-evaluation questionnaire). The intervention will take approximately 10 minutes to complete and is performed at Baseline Visit before IMP infusion. IMP is administered by IV infusion over 30 minutes (with possibility to extend the IV infusion by 15 minutes).

During the visits with IMP infusion, safety assessments will be performed before and after the infusion. The electronic patient-reported outcomes (ePROs) must be completed in the clinical

site at the visit date prior to the IV infusion. Participants must ensure to complete eDiary recording of headaches prior to the IV infusion (that is, for headaches which are ongoing or not yet recorded in the eDiary).

Participants who interrupt/terminate their IMP IV infusion are encouraged to attend all scheduled trial visits and trial procedures, including the Safety Follow-up to allow for application of treatment policy strategies. Participants who withdraw from treatment with IMP will not be replaced.

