- *all-participants-treated-open-label set (APTS-OL)* – all participants in the APRS who received an infusion of the IMP in the Open-label Period
- *all-participants-treated-follow-up set (APTS-FU)* - All participants in the APTS who are not in the APTS-OL, and who have data collected from the Safety Follow-up visit.

All data from the Placebo-controlled Period will be cleaned and the trial database for the Placebo-controlled Period will be locked when all participants have either completed or been withdrawn from the Placebo-controlled period. The participants and data will be classified into the analysis sets (APRS, APTS, and FAS) at a *Classification Meeting* held after the trial database for the Placebo-controlled Period has been released.

Data will be unblinded after the *Classification Meeting* for the sponsor and CRO functions involved in performing the analysis. All analyses specified in the SAP for data collected in the

Placebo-controlled Period will be performed. Sponsor and CRO functions that are in contact with the trial site staff, as well as clinical site staff and participants will remain blinded to individual participant treatment assignment through the end of the trial.

After all participants have completed the Open-label Period, the trial database for the full trial will be cleaned and locked. The participants and data will be classified into the analysis sets (APTS-OL and APTS-FU) according to these definitions. The defined population sets will be reviewed at a second *Classification Meeting* held after the full trial database has been released. The CTR will be issued after the end of the full trial completion.

Unless otherwise specified, the FAS will be used for all efficacy analyses in the Placebo-controlled Period, and the APTS will be used for all safety analyses in the Placebo-controlled Period, while the APTS-OL will be used for the safety and efficacy analysis of the Open-label Period. Relevant safety outputs for data collected at the Safety Follow-up visit for the APTS-FU will be listed.

5 Descriptive Statistics

In general, summary statistics (n, arithmetic mean, standard deviation [SD], median, lower and upper quartiles, minimum and maximum values) will be presented for continuous variables and counts and, if relevant, percentages will be presented for categorial variables.

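### SAP 3.3 rules out withdrawal from treatment, so the placebo-controlled row for TEAEs leading to it reads zero even if a Visit 2 reaction bars Visit 5

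*SAP*

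**What the plan says.** SAP 3.3 covers both periods: "Withdrawal from the treatment in the Placebo-controlled Period or the Open-label Period is not possible because IMP is only administrated once". It adds: "Note that the infusion interruptions or terminations before full dose is received are not related to withdrawal". Participants who do not leave the study before the open-label infusion are handled by one sentence: "The complementary group will be described as having completed the Placebo-controlled Period". Protocol 16.4 makes a narrower statement, for the placebo-controlled period only: "withdrawal from treatment is not possible for the APTS patients, as they only receive the treatment on one occasion".

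Other parts of the plan treat withdrawal from IMP as something that happens:

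- Protocol 5.4 has a list, separate from the study-withdrawal list, that opens "A patient must be withdrawn from further treatment with IMP if". One of its four conditions is that "the patient experiences an anaphylactic reaction or another serious and/or severe hypersensitivity reaction to the IMP infusion, as assessed by the investigator". Another is the investigator's judgement on safety, lack of efficacy or compliance.
- The protocol synopsis, in its disallowed-medication text under Target Patient Population, foresees a patient who has stopped IMP and remains in the study.
- SAP 2.1 says: "Participants who withdraw from treatment with IMP will not be replaced".
- SAP 3.2 and 12.1.3 make provision for participants with no Visit 5 infusion.

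On the output side, SAP 12.1.4 plans an overview entry, for the APTS and the APTS-OL, of TEAEs leading to withdrawal from treatment. SAP 12.1.7 carries the same term in its heading, but its text says only withdrawal, without naming treatment or study. SAP 18, which lists changes from the protocol, does not mention the point.

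**The concern.** The treatment course is two infusions, one at Visit 2 and one at Visit 5. SAP 3.3 looks at each infusion alone and concludes that nothing can be withdrawn. Protocol 5.4 looks at the course and requires the second infusion to be withheld after certain events. A decision taken during the placebo-controlled period not to give Visit 5 therefore has no place under the SAP definition.

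What is at stake is a standard tolerability entry. Hypersensitivity, including anaphylactic reactions, is a recognised adverse reaction of eptinezumab (protocol 1.1.3), and safety is a stated objective. A reader who sees zero against TEAEs leading to withdrawal from treatment will conclude that no reaction stopped dosing. Under 3.3 the zero would appear whether or not that was true.

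**Working it through.** The plan gives no figure on this point, so the check sets the texts side by side and follows a participant through the planned outputs.

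**1. Which protocol 5.4 conditions can matter.**
- Randomised in error without receiving IMP: the participant is outside the APTS, so not relevant.
- Code broken by site personnel before the open-label period: protocol 6.6 sends the patient to a Withdrawal Visit.
- Investigator's judgement: can apply to a treated participant who stays in the study. Only a decision made because of an adverse event bears on the TEAE outputs.
- Anaphylactic or other serious or severe hypersensitivity reaction: can apply to a treated participant who stays in the study.

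**2. A participant with an anaphylactic reaction at Visit 2, barred from Visit 5, who stays to Week 12.**
- SAP 3.3: not a treatment withdrawal; counted as having completed the placebo-controlled period.
- SAP 12.1.4, placebo-controlled: contributes 0 to the treatment-withdrawal entry.
- SAP 12.1.7: contributes 0 if the heading governs. If the text is read as study withdrawal, the contribution is also 0, because the participant stayed.
- SAP 12.1.1: appears in the AE listing, which includes *action taken with IMP*.
- SAP 12.1.10: appears in the AESI summaries and in the separate hypersensitivity and anaphylaxis listing.
- SAP 9 and 12.1.8: appears in the exposure and interruption outputs if the infusion was interrupted.

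**3. The same participant, but leaving the study at Week 8.** SAP 6.1 and 6.2 give a study-withdrawal reason. The 12.1.4 entry is still 0 under 3.3. The 12.1.7 count is 0 or 1, depending on whether the heading or the text is followed.

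**4. The open-label period.** After Visit 5 no further IMP is planned. Nothing is left to withdraw, so 0 is a fair entry.

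**5. How many participants.** The only rate in the documents that bears on a 5.4 condition is hypersensitivity of any grade in the pivotal studies: approximately 3% on 100 mg and 1% on placebo (protocol 1.1.3). With 285 randomised per arm:
- eptinezumab: 285 × 0.03 = 8.55, about 9;
- placebo: 285 × 0.01 = 2.85, about 3.

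These are not counts of treatment withdrawals. The serious or severe subset that triggers 5.4 is smaller, and anaphylaxis is described as rare. No rate is given for the investigator's judgement.

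**6. Completers without Visit 5.** SAP 6.1 reports placebo-controlled completers and the number treated in the open-label period. The first minus the second approximates the number who completed without Visit 5, after allowing for any randomised but untreated participants. It does not give reasons.

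**The case against.** The best defence is that 3.3 speaks of each period separately. One infusion is given per period, a completed infusion cannot be taken back, and for the placebo-controlled period the SAP follows protocol 16.4. Sections 12.1.4 and 12.1.7 do not cite 3.3, the AE data carry an action-taken field, and planning the output at all suggests that the sponsor means to fill it. The SAP 2.1 sentence is a non-replacement statement carried over from protocol 5.4, not an analysis definition.

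Part of this stands. The open-label zero is correct. For 12.1.7 the zero rests on the heading alone. A programmer may well populate the entry sensibly in practice. But 3.3 is the SAP's only definition of the term, it is categorical, and a decision not to give Visit 5 is made in the placebo-controlled period, where the definition denies it. The plan should not depend on a programmer setting its definition aside.

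A reader might also infer that completers without Visit 5 cannot be counted. The documents do not support that, because the subtraction in the working gives an approximate count. What is missing is a direct row and the reasons.

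**Conclusion.** The contradiction is in the text, and its effect is limited to safety reporting. Under 3.3 as written, the placebo-controlled treatment-withdrawal entry in 12.1.4, and 12.1.7 as headed, is zero whatever happens at Visit 2. This assumes that the programmer applies 3.3 literally, which the SAP gives no instruction to avoid.

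The number affected is unknown and probably small: some part of the roughly 9 and 3 any-grade hypersensitivity cases that the pivotal rates would imply, if they carry over, plus any safety decisions by investigators.

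A reader might infer that reactions would be hidden or the comparison between arms biased. Neither follows. The events remain in the AE listings, the AESI and hypersensitivity outputs and the infusion data. The primary analysis, power and type I error do not use this definition. It is a minor correction, worth making because it is nearly free and prevents a false zero.

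**What to change.** Replace the treatment-withdrawal statement in SAP 3.3 with: *Withdrawal from treatment in the Placebo-controlled Period is a decision under protocol 5.4, made after the Visit 2 infusion, that no further IMP will be given, whether or not the participant remains in the study. An interrupted or terminated infusion alone does not count.* A decision prompted by a reaction during the Visit 2 infusion is included. The clause on remaining in the study matters because a participant who is barred from IMP and leaves before Week 12 must still be counted.

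Then:
- derive the placebo-controlled outputs in 12.1.4 and 12.1.7 from *action taken with IMP*, checked against the Visit 5 infusion record;
- write *from treatment* in the text of 12.1.7;
- note the departure from protocol 16.4 in SAP 18.

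A 6.1 row for placebo-controlled completers without Visit 5 would be convenient but is optional, given the subtraction.

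The cost is SAP text and the programming of two outputs that are already planned. The action-taken field and the infusion data are already collected, although the documents do not show the field's response options, which should be confirmed. No clinical rule changes and no new data are needed.

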3.4 Definition of End-of-trial

The end of the trial for an individual participant is defined as the last protocol-specified contact with that participant.

The overall end of the trial is defined as the last protocol-specified contact with the last patient in the trial.

3.5 Definition of Planned versus Actual Treatment

Participants will receive either BI + eptinezumab 100 mg (EPTI), or BI + placebo (PBO) in the Placebo-controlled Period and eptinezumab 100 mg in the Open-label Period.

Planned treatment is defined as the treatment a participant was randomized to.

Actual treatment is defined as the treatment a participant actually received during the trial.

The term treatment group is used to denote which treatment (EPTI vs. PBO) participants received in the Placebo-controlled Period and in the Open-label Period. The term treatment sequence will be used to denote the treatment groups arising by combining the treatment received in the Placebo-controlled Period and eptinezumab 100 mg received in the Open-label

Period, i.e. the 2 groups are: PBO-uptinezumab 100 mg (PBO-EPTI) and EPTI-uptinezumab 100 mg (EPTI-EPTI).

For reporting purposes, the following will be summarized by planned treatment:

- Disposition
- Demographics and baseline characteristics
- Concomitant medication
- eDiary compliance
- Efficacy

And the following will be summarized by actual treatment:

- Exposure
- Adverse events
- Vital signs

Unless otherwise specified, safety data and concomitant medications data listings will be displayed using actual treatment sequence and other data listings will be displayed using planned treatment sequence.

3.6 Definition of Migraine, Headache Days

For the purpose of endpoint derivations, the following definitions of migraine and headache days will be used:

In this trial, the term headache will encompass both headaches and migraine headaches. Migraine headaches (henceforth simply referred to as “migraines”) are a subgroup of headaches with characteristics outlined below (Section 3.6.1). Using this definition, all migraines are headaches but not all headaches are migraines.

Headaches will be self-reported by the participant using an electronic headache diary on a daily basis from the time of screening until EoT/Withdrawal Visit. The eDiary is split into three parts: the headache diary, the aura without headache diary and the evening diary. The headache diary is the part of the eDiary where the start and stop date and times of experienced headaches are recorded along with headache characteristics and the intake of acute headache/migraine medication. Headache items will be assessed with a yes/no response; severity of pain will be rated as mild, moderate, or severe.

The headache diary is available all day. Participants are required to provide information on headache characteristics including associated symptoms and acute migraine medication intake on each day of an (ongoing) headache (either when a headache has ended or during the evening routine if the headache is ongoing).

The aura without headache diary is the part of the eDiary where data is collected on whether the participant experienced an aura without a headache and whether and what kind of acute headache medications were taken in relation to this event.

The evening diary is the part of the eDiary, that participants are expected to complete each evening. It collects data on acute migraine medication that was taken preventively and triggers the evening routine including the headache and aura without headache diaries.

Panel 3 IHS ICHD-3 Guidelines for Migraine

1.1 Migraine without aura	1.2 Migraine with aura
A. At least five attacks fulfilling criteria B to D	A. At least two attacks fulfilling criteria B and C
B. Headache attacks lasting 4 to 72 hours (when untreated or unsuccessfully treated)	B. One or more of the following fully reversible aura symptoms: 1. visual 2. sensory 3. speech and/or language 4. motor 5. brainstem 6. retinal
C. Headache has at least two of the following four characteristics: 1. unilateral location 2. pulsating quality 3. moderate or severe pain intensity 4. aggravation by or causing avoidance of routine physical activity (for example walking or climbing stairs)	C. At least three of the following six characteristics: 1. at least one aura symptom spreads gradually over ≥ 5 minutes 2. two or more aura symptoms occur in succession 3. each individual aura symptom lasts 5–60 minutes 4. at least one aura symptom is unilateral 5. at least one aura symptom is positive 6. the aura is accompanied, or followed within 60 minutes, by headache
D. During headache at least one of the following: 1. nausea and/or vomiting 2. photophobia and phonophobia	D. Not better accounted for by another ICHD-3 diagnosis
E. Not better accounted for by another ICHD-3 diagnosis	
